13.0 CRITERIA FOR REMOVAL FROM STUDY

In accordance with the Declaration of Helsinki, ICH Good Clinical Practice Guidelines, and the US FDA Regulations, a patient has the right to withdraw from the study at any time for any reason without prejudice to his/her future medical care by the physician or at the institution. The Investigator also has the right to withdraw patients from the study (see below). Should a patient (or a patient's legally authorized representative) decide to withdraw, all efforts will be made to complete and report the observations as thoroughly as possible.

A complete final evaluation should be made at the time of the patient's withdrawal, the Study Status Outcome form in the case report form should be completed with an explanation of why the patient is withdrawing, and an attempt should be made to perform a follow-up evaluation.

Patients may be removed from study if one or more of the following events occur:

- Significant noncompliance on the part of the patient
- Refusal of the patient to continue treatment or observations
- Unacceptable toxicity (i.e.: grade 3-4 toxicity related to CMV CTL infusion). Removal for unacceptable toxicity does not necessarily preclude continued follow-up.
- Progressive disease that in the Investigator's opinion requires therapeutic intervention that would interfere with the interpretation of results from the study
- Decision by the Investigator that termination is in the patient's best medical interest
- Unrelated medical illness or complication
- Lost to follow-up.

14.0 BIOSTATISTICS

A phase 2 trial design will be applied to determine the efficacy and safety of CMV specific T cells for the treatment of marrow transplant patients with CMV. The endpoint of this study is complete response, defined as the clearance of the CMV infection 3-7 weeks following completion of the last cycle of CMV CTLs. The evaluation of treatment efficacy will be assessed for patients receiving CMV specific T cells from their transplant donor. It is anticipated that accrual will be completed within 3 years.

A two-stage design with a maximum of 39 patients will be employed. The study design discriminates between population response rates of 0.50 and 0.70. In the first stage, 23 patients will be enrolled in the study. If 11 or fewer complete responses (CRs) are observed, then the trial will be stopped. If at least 12 complete responses are observed, then 16 additional patients will be accrued. At the conclusion of the trial, if 23 or fewer CRs are observed, we will conclude that the treatment is not sufficiently active. This design has power 0.90 for a population CR rate equal to 0.70 using a one-sided test with type 1 error equal to 0.10.

The probability of a complete response and the proportion of patients requiring ganciclovir or foscarnet will be computed.

Following approval of Amendment 22, additional accrual on study is anticipated to be 2-3 patients per year, for an additional 3 years, for a target accrual of approximately 7 additional patients. As the accrual will be lower than the originally targeted accrual number, there will be no hypothesis test for efficacy analysis and the efficacy analysis is to estimate the complete response (CR) rate with its 80% confidence interval. For example, with 9 CR observed among a total of 15 subjects, the estimate of CR rate is 60% with the 80% Clopper-Pearson exact confidence interval of (40.4%, 77.4%).

The effects of infusing activated CMV-specific T-cells on the general immune function of the host will be assessed by recording CD4⁺ and CD8⁺, CD3⁺ T-cells, NK cells and B-cells prior to and one week following each course of cell infusions and 1, 2 and 4 months following completion of the second course of cells. In addition, the levels of CMV DNA and T cells generating IFNg in response to the CMV pentadecapeptides will be measured weekly for the first 8 weeks and then monthly until 6 months post infusion. Nonparametric smoothing will be used to estimate the population trajectory of these response curves over time. In addition, a generalized estimating equation approach will be used to model the relationship between the immunologic reconstitution factors and complete response.

In order to reduce patient risk, the study design includes early termination in the event of excessive graft versus host disease during the accrual period. The stopping rule for excessive GvHD and the corresponding power calculation will be applied separately for the two donor groups. In the event that the stopping boundary is crossed for one of these groups, the study will continue accrual in the other group.

Allo donor

Failure type	# of failures needed to stop the study	Failure rate in the population	Probability boundary is crossed
Acute GvHD (grades 3-4)	3 within the first 15 patients	0.06	0.10
	4 within the first 24 patients		0.90
	5 within the first 35 patients	0.20	
	6 within 39 patients		
Chronic GvHD (extensive)	3 within the first 15 patients	0.06	0.10
	4 within the first 24 patients		0.90
	5 within the first 35 patients	0.20	
	6 within 39 patients		

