9.1 Treatment with CMVpp65 Specific T-cells

Eligible patients who consent to enter this trial and for whom CMV-pp65 CTLs are available, will receive 3 weekly infusions of CMV-pp65 CTLs. The T cells will be administered immediately after thawing. The final product is cryopreserved in a volume of 1-2 ml. This will be drawn up in a sterile syringe containing 30 ml of normosol for intravenous administration and administered by slow intravenous infusion ideally over approximately 5 minutes.

In this phase II trial, patients will be treated at doses of 1×10^6 CMVpp65-CTL/kg/dose/week for 3 weeks (+/- 20% variability of total dose). Patients will be observed for the following 3 weeks. Additional 3 week courses of CMVpp65-CTL may be administered if levels of CMV DNA in blood are still detectable despite disease stabilization or improvement.

If the planned dose of CMV peptide sensitized T-cells is not achieved, but the cells generated exhibit required levels of CMV specific cytotoxic activity and meet all other release criteria, the T-cell product may be administered at a lower dose level.

In certain cases, in order to avoid refreezing of the final product to achieve a specific dose level, which may affect viability, variability of each dose may exceed +/-20%. In such cases, care will be given to ensure that the total combined volume of the 3 doses does not exceed the planned dose.

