- Flow Cytometry 7 panel to enable quantification of CD4 and CD8 T cell number may be obtained prior to the first infusion, on day 14, week 4, and week 8 post-initial infusion with CMV-specific T-cells, then monthly until 6 months post initial infusion
- T cell populations and their responses to mitogens and to candida albicans antigen should be obtained pre-initial infusion and may also be monitored at approximately 2, 4, and 6 months post initial infusion as a measure of general immune function.
- Patients with CMV pneumonia should be monitored by at least daily measurements of blood gases and/or O₂ saturations until normalized and weekly chest films together with CT scans at pre-infusion and approximately every 2-4 weeks until clear.
- Ophthalmologic evaluations will be made to document responses of CMV retinitis. These evaluations will ideally be done every 2 weeks.
- Patients with known CMV enteritis should be monitored by approximately three times weekly measurements of 24 hour stool volumes, stool guaiacs and cultures for CMV. If acceptable to the patient, colonoscopy should be repeated approximately three weeks after the dose of T cells to assess response.
- If the CMV infection affects the CNS, lung, or abdominal organs, and virus has been detected (e.g.: in pleural or peritoneal fluids), appropriate tissue and/or CSF may be collected (if indicated and possible) and tested for the presence of CMV and CMV specific T-cells. These tests should occur between 3-6 weeks post initiation of treatment, whenever possible.

APPROXIMATE SCHEDULE OF PATIENT EXAMINATIONS AND STUDIES

Evaluations	Pre-Infusion	Day 0 > 1	Day 7	Day 14	Day 15	Wk 3	Wk 4	Wk 5	Wk 6	Wk 7	Wk 8	Mo 3	Mo 4	Mo 5	Mo 6
History, Review of Systems, & Physical Exam (incl. GVHD eval) ¹	x	x	x	x	x	x	x	x	x	x	x	x	x	x	x
CBC/CMP	x	x	x	x	x	x	x	x	x	x	x	x	x	x	x
CMV PCR (10 ccs)	x	x	x	x	x	x	x	x	x	x	x	x	x	x	x
T cell Immunophenotype short panel	X			X			X				X	x	x	x	x
Mitogens (PHA)	X											X		X	
Antigen (Candida albicans)	X											X		X	
Research Bloods	X	x	x	x	x	x	x	x	x	x	x	x	x	x	x
Immune Monitoring ³	X		x	x		x	x	x	x	x	x	x	x	x	x
Chest X-Ray and/or CT (if indicated)	x														
EKG (if indicated)	x														
Ophthalmologic exam (if indicated)	x														
Colonoscopy (if indicated)	x														
Cultures of affected body fluids and/or tissue (if possible/indicated)	x					x									
Treatment CMV Specific T-cells ²		x	x	x											

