¹ GVHD evaluations to be performed weekly until Week 8 and a consensus at Day 100

² If patient is given additional cycles of CMV specific T-cells, calendar will restart from Day 0. Doses are given weekly and can be held at the discretion of the PI or in the case of severe toxicity related to infusion.

³ Prior to and at specific intervals following infusion of CMVpp65-CTL, patients will be monitored for levels of CMVpp65-CTL in the blood as measured by quantitation of CTL precursor frequencies, CMV pp65-specific IFNy+ T-cells (35), or epitope specific-T-cells binding HLA-peptide tetramers and their V β usage (36). The third party T-cells will also be monitored by analysis of CMVpp65 IFNy+ T-cells as to their genetic origin.

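### Section 14 dates the late lymphocyte-subset counts from an optional second course, so a patient given one course has no late subset count in the planned analysis

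*Combined protocol and SAP*

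**What the plan says.** Section 14.0 assesses general immune function from CD3, CD4, CD8, NK and B cell counts. They are to be recorded "prior to and one week following each course of cell infusions", and then "1, 2 and 4 months following completion of the second course of cells".

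The planned treatment is one course of three weekly infusions followed by three weeks of observation (Sections 4.3 and 9.1). A further course is conditional: "Additional 3 week courses of CMVpp65-CTL may be administered if levels of CMV DNA in blood are still detectable despite disease stabilization or improvement".

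Section 10.0 uses a different clock. The flow panel is timed "prior to the first infusion, on day 14, week 4, and week 8 post-initial infusion", then monthly to month 6 from the initial infusion, with no distinction by number of courses. The schedule table shows the same visits. A separate Section 10 item says that T-cell populations and their mitogen and antigen responses "may also be monitored at approximately 2, 4, and 6 months post initial infusion as a measure of general immune function". Footnote 2 to the table adds that, if more cycles are given, the "calendar will restart from Day 0".

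For CMV DNA and IFN-gamma-producing T cells, Section 14 says they are "measured weekly for the first 8 weeks and then monthly until 6 months post infusion". Section 10 times both from the initial infusion.

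**The concern.** The late subset counts hang on an event that many patients may never have, and whether they have it depends on how they responded. A patient who clears CMV after one course has no reason under the protocol to receive a second. A patient who progresses is outside the condition the text gives for one. What remains is the middle group: stable or improved, with DNA still detectable, who then complete course two.

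A late description built on that group would not describe the treated population. Section 14 also plans a GEE model relating immune reconstitution factors to complete response. If late subset counts enter it as Section 14 dates them, everyone who reached complete response after a single course is missing from that part of the comparison, although complete response is the other variable in the model.

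The sections also give no single time zero: completion of course two (Section 14), the initial infusion (Section 10), or Day 0 of the latest cycle (footnote 2).

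**Working it through.** The plan states no figure that depends on this timing, so there is none to reproduce. The check is calendar arithmetic and a comparison of the sections.

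**Inputs.** Doses on days 0, 7 and 14 (schedule table); three weeks of observation (Section 9.1). Assumptions: one month = 30.4 days (365.25/12), and a course ends either at the third dose (day 14) or after three full weeks (day 21), because the documents do not say which.

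**One-course patient.**
- Section 14 early counts: before the course, and one week after it, at 14 + 7 = day 21 or 21 + 7 = day 28. That is 2 time points.
- Section 14 late counts: no date, because there is no second course to complete.
- Section 10 panels: pre-infusion, days 14, 28 and 56, then months 3 to 6 at 3, 4, 5 and 6 × 30.4, or about days 91, 122, 152 and 183. That is 8 panels, 5 of them after day 28. Section 14 names none of those 5.
- The table has a panel at week 4 (day 28) and none at week 3 (day 21), so the one-week count matches a scheduled panel only on the second definition of course end.

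**Two-course patient, in days from the restarted Day 0.** Restarted panels fall on days 14, 28, 56, 91, 122, 152 and 183.

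| Section 14 late point | Course ends day 14 | Nearest panel (gap) | Course ends day 21 | Nearest panel (gap) |
|---|---|---|---|---|
| 1 month | 44 | 56 (12 days) | 51 | 56 (5 days) |
| 2 months | 75 | 91 (16 days) | 82 | 91 (9 days) |
| 4 months | 136 | 122 (14 days) | 143 | 152 (9 days) |

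The earliest restart is 14 + 21 = day 35 or 21 + 21 = day 42 from first infusion. The last restarted panel then falls at 35 + 183 = day 218 or 42 + 183 = day 225 from first infusion.

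**Who has a late subset count under Section 14.**
- Cleared after course one: no second course, no late count.
- Progressed: outside the stated condition for a further course, no late count.
- Stable or improved with DNA detectable: a late count only if a second course is given and completed.

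**Other measures.** CMV DNA and IFN-gamma T cells carry no second-course condition in either section. Their only loose end is the footnote 2 restart, in patients given more than one course.

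**Number affected.** The documents give no share of patients receiving a second course. In the 15-patient example in Section 14 it could be anything from 0 to 15. That example has 9 complete responses but does not say after how many courses.

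**The case against.** The strongest reply is that Section 10 schedules the panels through month 6 whatever the number of courses, so the data can exist, and Section 14 nowhere forbids using them. That stands against the tempting inference that one-course patients will have no late counts at all. The documents do not support that inference, although Section 10 says only that the "Flow Cytometry 7 panel to enable quantification of CD4 and CD8 T cell number may be obtained". What remains is that Section 14 names a different set of time points, and choosing among panels after the results are seen is what a prespecified analysis is meant to prevent.

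A reader might also infer that every late comparison of immune factors with complete response loses the one-course responders. It does not: IFN-gamma T cells are scheduled to month 6 without a second-course condition and are plausibly among the factors meant. The same fact defeats the inference that CMV DNA and IFN-gamma T cells share the gap. The planned smoothing is probably unaffected too, since the curves it refers to most naturally mean the CMV DNA and IFN-gamma measurements in the sentence just before.

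It may be said that second simply means last. Section 14 writes of the last cycle when defining its endpoint, so the wording differs within the section. Even on that reading, timing from completion still has to be aligned with the Section 10 visits.

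Finally, Section 10 calls its timing approximate, so gaps of 5 to 16 days carry little weight alone. That is fair. The main fault is the undefined late count, not the offset.

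**Conclusion.** The point holds for the lymphocyte subsets and is minor. Followed literally, Section 14 gives a one-course patient no late subset count and limits the late subset description to a response-selected group. The same limit applies to the GEE model only so far as late subset counts enter it, and Section 14 does not list the factors.

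General immune function is not among the objectives in Section 2.0, so this is a supportive analysis. The complete response estimate and the GvHD stopping rule do not depend on it.

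The number of patients affected cannot be computed. A reader might try to derive it from the phase I clearance results in Section 3.0, but those do not state how many courses were given or when clearance was measured, so they give no usable bound.

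The conclusion rests on reading the second-course clause as written and on further courses being given only in the circumstance Sections 4.3 and 9.1 describe. The day counts rest on the month length and the two definitions of course end given with the calculation.

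**What to change.** In Section 14, replace the second-course clause with wording such as: *and, in all treated patients, at the Section 10 panel visits (day 14, weeks 4 and 8, months 3 to 6), analysed by actual time since the first infusion of the first course, with the start of any further course recorded and marked.* Add to footnote 2 that the restart sets visit dates and not the analysis time zero, and apply this to CMV DNA and IFN-gamma T cells in patients given more than one course.

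Three smaller items go with this:
- Say which day is one week after a course, and align it with a scheduled panel. Day 28 needs no new visit; day 21 would need a week-3 panel added to the table.
- Confirm that the panel reports NK and B cells, since the Section 10 flow item mentions only CD4 and CD8.
- Report how many patients contribute at each time, because the panel is optional in Section 10.

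A workable alternative is to change second to last course. That defines late counts for every patient and keeps a post-treatment anchor, but the visits must then be aligned with the Section 10 calendar.

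The cost is wording and minor programming. The downside is real but small: in patients given further courses, visit times become irregular on the first-infusion scale, and the three post-completion time points are replaced by scheduled panels 5 to 16 days away. Late estimates from few patients will remain imprecise.

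### The GvHD stopping table still gives 39-patient crossing probabilities although accrual will end below 39, and its text refers to two donor groups where the plan has one

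*Combined protocol and SAP*

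**What the plan says.** Section 14.0 was written for a fixed maximum: "A two-stage design with a maximum of 39 patients will be employed". The GvHD table in the same section has one block, labelled Allo donor. For acute GvHD of grades 3-4, and identically for extensive chronic GvHD, the boundary is 3 failures within the first 15 patients, 4 within 24, 5 within 35, and finally "6 within 39 patients". Against this the table sets a crossing probability of 0.10 at a population rate of 0.06 and 0.90 at a rate of 0.20. The column heading counts the failures that stop the study.

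The Amendment 22 paragraph changes the expected size. It foresees 2-3 patients a year for three more years, "for a target accrual of approximately 7 additional patients". It continues: "As the accrual will be lower than the originally targeted accrual number", "there will be no hypothesis test for efficacy analysis", and efficacy becomes an estimate with an 80% confidence interval. The number already treated is not given. The only total mentioned is an illustration of the interval: "For example, with 9 CR observed among a total of 15 subjects".

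The paragraph introducing the GvHD table says: "The stopping rule for excessive GvHD and the corresponding power calculation will be applied separately for the two donor groups". If one group crosses, "the study will continue accrual in the other group".

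**The concern.** Two parts of the stopping text no longer match the current design.

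**Crossing probabilities.** The chance that a sequential boundary is crossed depends on how many patients pass through it. If accrual ends early, the later steps cannot act and the chance of stopping at a truly excessive GvHD rate falls. The plan adapted its efficacy analysis to the lower accrual but left the safety probabilities as they were. GvHD risk is the second primary objective (section 2.0), and this table is the only numerical safety boundary in the plan. A safety committee or ethics board reading it would take away a 90% chance of stopping at a 20% rate of severe GvHD.

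**Donor groups.** Sections 4.2, 9.2 and 9.3, inclusion criterion 3 in section 6.2.1, and the efficacy paragraph of section 14.0 all describe one treated group: patients given cells from their own transplant donor. A rule run separately in two groups, with one continuing after the other crosses, contradicts that. It also sits badly with the table heading, under which crossing stops the study. An early-termination rule should not leave its own consequence open.

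**Working it through.** **Inputs (all from section 14.0).** Boundary: 3 failures up to patient 15, 4 up to patient 24, 5 up to patient 35, 6 up to patient 39. True failure rates p = 0.06 and p = 0.20. Stated crossing probabilities 0.10 and 0.90. Original maximum 39; current total below 39 but not stated.

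**Method.** Exact binomial recursion. Let P(n, k) be the probability of k failures among n patients with no crossing so far. Then

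P(n, k) = (1 − p) · P(n−1, k) + p · P(n−1, k−1).

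After each patient, all probability at or above the boundary count for that n is removed and added to the crossing probability. Checking only at 15, 24, 35 and 39 patients gives the same results at those totals.

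**Step 1: the first boundary by hand.** With 15 patients, crossing means at least 3 failures, so the probability is 1 − P(0) − P(1) − P(2):

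- p = 0.06: 1 − (0.3953 + 0.3785 + 0.1691) = 1 − 0.9429 = 0.0571
- p = 0.20: 1 − (0.0352 + 0.1319 + 0.2309) = 1 − 0.3980 = 0.6020

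**Step 2: reproduce the plan's figures.** The full recursion to 39 patients gives 0.1011 at p = 0.06 and 0.8958 at p = 0.20. These round to the stated 0.10 and 0.90, so the table is correct for 39 patients.

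**Step 3: same boundary, accrual ending earlier.** Every total below 39 is an assumption, because the documents do not give the final number.

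| Total treated | Crossing at 6% | Crossing at 20% | 0.90 minus crossing at 20% |
|---|---|---|---|
| 15 | 0.0571 | 0.6020 | 0.298 |
| 20 | 0.0633 | 0.6705 | 0.230 |
| 24 | 0.0794 | 0.7697 | 0.130 |
| 30 | 0.0847 | 0.8182 | 0.082 |
| 32 | 0.0894 | 0.8454 | 0.055 |
| 34 | 0.0958 | 0.8718 | 0.028 |
| 35 | 0.0996 | 0.8842 | 0.016 |
| 36 | 0.0996 | 0.8842 | 0.016 |
| 37 | 0.0999 | 0.8865 | 0.014 |
| 38 | 0.1004 | 0.8905 | 0.010 |
| 39 (original) | 0.1011 | 0.8958 | 0.004 |

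The values apply to each GvHD type separately. At 38 patients the probability at 20% already rounds to 0.89. The false-stop probability at 6% stays at or below its 39-patient value, so only the sensitivity suffers.

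**Step 4: donor groups.** No arithmetic applies. Section 9.3 provides only for cells from the patient's transplant donor, and section 9.2 defines the subjects in the same way. Sections 5.1 and 6.2.3 list three groups of cell donors, but those are sources of cells, partly for third-party use in other patients, and not treated cohorts of this trial. The table has one block. No second group exists in which accrual could continue.

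**The case against.** The strongest reply has four parts.

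*Nothing is miscalculated, and the table shows its own basis.* The last row names 39 patients, and the Amendment 22 paragraph says openly that accrual will be lower. It is true that the arithmetic is right for 39. But a reader cannot derive the present sensitivity from the table, and the plan does not give the total needed to work it out.

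*The rule still works.* Each step acts on patients as they accrue, whatever the final number. GvHD is also assessed weekly to week 8 with a consensus at day 100 (section 10.0), tracked at any time after infusion (section 11.0), and the institutional data and safety monitoring committee reviews the trial (section 16.3). This stands: neither the boundary nor patient exposure is affected.

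*The size is unknown and whole-trial figures are of limited use.* Some patients were treated before Amendment 22, and their events count towards the boundary. Suppose, purely as an illustration, 8 patients already treated, a total of 15 and a true rate of 20%. The chance of crossing in the last 7 is then 0.148, 0.423 or 0.790 with 0, 1 or 2 earlier events. This also stands. It limits what the restated figures mean, but it does not make the stated 0.90 applicable. For the same reason, 0.60 at 15 patients must not be quoted as this trial's sensitivity, since 15 is only the plan's example.

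*The donor-group wording is harmless*, because with one group the practical reading is that the study stops. That is the likely reading, but the text of a stopping rule should say it.

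**Conclusion.** The concern holds, and section 14.0 is wrong as written on both counts.

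The stated 0.90 is a property of the 39-patient design, which the plan itself says will not be reached. The shortfall against 0.90 is 1 to 2 percentage points at 35-38 patients, 3 at 34, 5 at 32, 8 at 30 and 13 at 24. It is therefore slight if accrual ends near 35 or above and material only clearly below that. The mismatch is certain; its size rests on a total that the documents do not give.

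The donor-group contradiction does not depend on the total. It leaves unclear whether crossing the boundary ends the study.

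Both should be corrected, but neither undermines the boundary or changes what happens to patients already on it.

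**What to change.** In section 14.0:

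1. State the expected total after Amendment 22, that is, the number already treated plus about 7.
2. Label 0.10 and 0.90 as the values for 39 patients. Beside them, give the exact crossing probabilities for the expected total, or for a short range of totals as in the table above. Say that these are whole-trial probabilities counted from the first patient.
3. Keep the boundary rows; this point gives no reason to alter them.
4. Reconcile the two donor-group sentences with the single transplant-donor group and with the table heading, so that the consequence of crossing is stated once and without ambiguity.

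The cost is a few sentences and one recalculation. No patients or analyses are added. The only drawback is that the stated safety sensitivity will look less favourable than 0.90.
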